6.3.1 Potential drug-induced liver injury IMP discontinuation criteria

Subjects with potential drug-induced liver injury (PDILI) must be assessed to determine if IMP must be discontinued. In addition, all concomitant medications and herbal supplements that are not medically necessary should also be discontinued.

The PDILI criteria below require immediate discontinuation of IMP:

- Subjects with either of the following:
 - ALT or AST $\geq 8xULN$
 - ALT or AST $\geq 3xULN$ and coexisting total bilirubin $\geq 2xULN$
- - Subjects with ALT or AST $\geq 3xULN$ who exhibit temporally associated symptoms of hepatitis or hypersensitivity. Hepatitis symptoms include fatigue, nausea, vomiting, right upper quadrant pain or tenderness. Hypersensitivity symptoms include fever (without clear alternative cause), rash, or eosinophilia (ie, $>5\%$).

If a nondrug-related cause for the symptoms can be confirmed, these subjects may resume IMP administration after discussion with the responsible UCB physician, but only when the requirements for rechallenge with IMP as provided in [Section 12.2.1.2.1](#) are followed.

The PDILI criterion below allows for subjects to continue on IMP at the discretion of the Investigator.

- Subjects with ALT or AST $\geq 5xULN$ and $<8xULN$, total bilirubin $<2xULN$, and no eosinophilia (ie, $\leq 5\%$), with no fever, rash, or symptoms of hepatitis (eg, fatigue, nausea, vomiting, right upper quadrant pain or tenderness).

Evaluation of PDILI must be initiated as described in [Section 12.2.1](#) with repeat tests performed in 2 weeks. Upon retest, if ALT or AST values have reduced to $<5xULN$, the subject can continue with the study. However, if ALT or AST remains $\geq 5xULN$ $<8xULN$ after retest, IMP should be temporarily withheld and subject should undergo a repeat test in 2 weeks. The subject will continue to be monitored at least twice per week until values normalize, stabilize, or return to within baseline values. If ALT or AST values remain $\geq 5xULN$ even after the second retest, then the subject should be permanently withdrawn from the study and should be followed for possible PDILI.

If subjects are unable to comply with the applicable monitoring schedule, IMP must be discontinued immediately.

Investigators should attempt to obtain information on subjects in the case of IMP discontinuation to complete the final evaluation. Subjects with PDILI should not be withdrawn from the study until investigation and monitoring are complete. All results of these evaluations and observations, as well as the reason(s) for IMP discontinuation and subject withdrawal (if applicable), must be recorded in the source documents. The eCRF must document the primary reason for IMP discontinuation.

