9. A subject considered as having either a suspected new LTB infection or who develops active TB or NTMB infection during the study (including but not limited to, conversion demonstrated by IGRA or other diagnostic means) must be immediately discontinued from IMP, an ET Visit must be scheduled as soon as possible, but not later than the next regular visit.

The subject must be permanently withdrawn if further examinations result in a diagnosis of active TB, or if the subject is diagnosed with LTB infection with no initiation of prophylactic treatment, prematurely discontinues prophylactic treatment, or, in the opinion of the Investigator or Sponsor, is noncompliant with prophylactic TB therapy.

Confirmed active TB is an SAE and must be captured in the electronic Case Report Form (eCRF) in the SAE Report Form section. As with all SAEs, periodic follow-up reports should be completed as per protocol requirements until such time as the TB infection resolves.

Additional information on TB policies is provided in [Section 12.3.6](#).

10. Subjects with newly diagnosed IBD or with IBD flares during the study must:

- Be referred, as appropriate, to a health care professional treating IBD, such as a gastroenterologist
- Discontinue IMP and be followed-up until resolution of active IBD symptoms

If IBD flares increase in severity or frequency during the study, the Investigator should use clinical judgment in deciding whether the subject should continue on IMP and contact the Medical Monitor and UCB study physician to confirm the subject's suitability for continued participation in the study.

11. Subjects **must be referred** immediately to a mental health care professional and may be withdrawn from the study based upon the Investigator's judgment of benefit/risk for:

- Active suicidal ideation as indicated by a positive response (“Yes”) to Questions 4 of the “Since Last Visit” version of the eC-SSRS
- Moderately severe major depression as indicated by a PHQ-9 score of 15 to 19 if this represents an increase of 3 points compared to last visit

The mental health consultation must be recorded in the subject's source documentation.

12. Subjects **must be referred** immediately to a mental healthcare professional and must be withdrawn in case of:

- Active suicidal ideation as indicated by a positive response (“Yes”) to Question 5 of the “Since Last Visit” version of the eC-SSRS.
- Any suicidal behavior since the last visit.

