≥5xULN (and ≥2x baseline) and <8xULN	<2xULN	No	
Discussion with Medical Monitor required.
 
Consider need for hepatology consult if there is no evidence of resolution (see Follow up requirements).^c
	
Further investigation – immediate IMP discontinuation not required (see Section 12.2.1.2).
 
IMP discontinuation required if any of the following occur:
 
 • Subject cannot comply with monitoring schedule. • Liver chemistry values continue to increase. • Liver chemistry values remain ≥5xULN (and ≥2x baseline) after 4 weeks of monitoring without evidence of resolution. 	
Essential: Every attempt must be made to have repeat liver chemistry values and additional testing completed within 48 hours at the site with HCP (see Section 12.2.1.3).
	
Monitoring of liver chemistry values at least twice per week for 2 weeks.^c
 
 • Immediate IMP discontinuation required if liver chemistry values continue to increase. 
After 2 weeks of monitoring liver chemistry values:
 
 • ALT or AST remains ≥5xULN <8xULN, IMP should be temporarily withheld and subject should undergo repeat test in 2 weeks. • Continue IMP if ALT or AST values <5xULN; continue to monitor at least twice per week until values normalize, stabilize, or return to within baseline values.

Table 12–3: Required investigations and follow-up for PDILI

Laboratory value			Immediate		Follow up	
ALT or AST	Total bilirubin	Symptoms ^a of hepatitis of hypersensitivity	Consultation requirements	Actions	Testing	Evaluation
						
 If ALT or AST remains $\geq 5 \times \text{ULN}$ after second re-test, immediate IMP discontinuation required. Continue to monitor until values normalize, stabilize, or return to within baseline values. ^e

ALP=alkaline phosphatase; ALT=alanine aminotransferase; ASAP=as soon as possible; AST=aspartate aminotransferase; HCP=healthcare practitioner; IMP=investigational medicinal product; NA=not applicable; PDILI=potential drug-induced liver injury; ULN=upper limit of normal

^a Hepatitis symptoms include fatigue, nausea, vomiting, and right upper quadrant pain or tenderness; hypersensitivity symptoms include eosinophilia (>5%), rash, and fever (without clear alternative cause).

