12.3.6.4 Tuberculosis management

LTB infection and active TB identified during study

During the study, subjects who develop evidence of LTB infection or active TB must immediately stop further administration of IMP and will be referred to an appropriate TB specialist (pulmonologist or infectious disease specialist) for further evaluation. Evidence of LTB infection is defined as subject’s IGRA test converts to positive or indeterminate (and confirmed indeterminate on repeat), or the subject’s questionnaire or history and physical

indicates that TB infection or exposure may have occurred. Evidence of active TB includes, in addition to the aforementioned tests, signs and symptoms of organ involvement. In either situation, the subject should be carefully assessed by a TB specialist for active TB. Subjects diagnosed with active TB should be withdrawn from the study and receive appropriate TB or prophylaxis therapy.

If a TB specialist excludes an active TB infection, the subject can proceed with the IMP no earlier than 4 weeks after the start of an appropriate prophylactic therapy.

Any presumptive diagnosis or diagnosis of a TB infection is a reportable event. Confirmed active TB must be reported as an SAE. The Investigator is to complete and submit the TB follow-up form provided.

The subject should be transferred to the care of his/her physician and managed according to the best available standard of care. Subjects identified as having converted to active TB during the study must be withdrawn and scheduled to return for the ET Visit as soon as possible but no later than the next scheduled study visit and complete all ET Visit assessments.

The subject should be encouraged to complete a SFU Visit (20 weeks after the final dose of IMP).

If infection with NTMB is identified during the study, the same procedure as for active TB acquired during the study must be followed.

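### Protocol stopping rules for liver injury, IBD and TB conflict on stopping IMP, resuming it or leaving the study, and must be reconciled; the effect on the primary analysis is limited

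*Protocol*

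**What the plan says.** All of the following stands in current Protocol text, not in the amendment summaries.

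**Common rule.** The lead-in to items 1 to 13 of Section 6.3 takes subjects off IMP and has them return for the remaining visits up to Week 16 and for the SFU Visit. Item 5a (hepatotoxicity, referring to 6.3.1), item 9 (TB) and item 10 (IBD) all fall under it.

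**Liver, ALT or AST 5 to <8xULN without symptoms.** Section 6.3.1 allows IMP to continue at the Investigator's discretion, withholds it if the first retest is still in that band, and at a second retest still at least 5xULN says "then the subject should be permanently withdrawn from the study and should be followed for possible PDILI". The same section adds: "Subjects with PDILI should not be withdrawn from the study until investigation and monitoring are complete". For the same second-retest result, Table 12-3 requires IMP discontinuation with continued monitoring. Table 12-3 also enters subjects only if the value is at least twice baseline, and stops IMP if values keep rising. Section 6.3.1 has neither condition.

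**IBD (item 10).** Subjects with new IBD or a flare must "Discontinue IMP and be followed-up until resolution of active IBD symptoms". If flares become more severe or frequent, "the Investigator should use clinical judgment in deciding whether the subject should continue on IMP".

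**TB.** Under item 9 a subject with even a suspected new latent infection "must be immediately discontinued from IMP, an ET Visit must be scheduled as soon as possible". Section 12.3.6.1 sends latent or active TB to the study's withdrawal procedures. Section 12.3.6.4 says that once active TB is excluded "the subject can proceed with the IMP no earlier than 4 weeks after the start of an appropriate prophylactic therapy", and footnote b of Figure 12-2 likewise lets subjects with latent infection continue.

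**Analysis.** Section 14.3.1.1 defines the intercurrent event as discontinuing study treatment before Week 16. It counts data after that event, and any other missing Week 16 result, as nonresponse.

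**The concern.** These are mandatory safety rules, and for one and the same finding the text gives a site different actions: stop the drug, let the Investigator decide, or remove the subject from the study. Safety execution is the main thing at stake.

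The statistical stake follows from the definitions. Stopping IMP is the intercurrent event, and leaving the study loses the Week 16 assessment. Where two passages differ on stopping versus continuing IMP, a subject could be analysed as observed at one site and as a nonresponder at another. For continuous endpoints the switch is between an observed and an imputed value. Where they differ only on leaving the study, the loss is the off-treatment Week 16 value used by the treatment-policy analysis in Section 14.7.

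**Working it through.** **Step 1. Compare the outcomes, branch by branch.**

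| Situation | One text | Another text | Intercurrent-event status differs? |
|---|---|---|---|
| Second retest at least 5xULN | 6.3.1: leave the study | Table 12-3 and 6.3 lead-in: stop IMP, monitoring and visits go on | No; IMP ends under both |
| Values rising within 5 to <8xULN | 6.3.1: may continue until the 2-week retest | Table 12-3: stop IMP | Can differ |
| At least 5xULN but below 2x baseline | 6.3.1 band applies | Table 12-3 row not met | Can differ |
| IBD flare that worsens | Item 10: stop IMP | Item 10: judgment on continuing | Can differ |
| Latent TB | Item 9 and 12.3.6.1: ET Visit, withdrawal procedures | 6.3 lead-in, Figure 12-2 note b, 12.3.6.4: visits go on, IMP may resume | Can differ, or is undefined |
| Active TB | 6.3 lead-in: stop IMP, visits go on | 12.3.6.4: leave the study | No |

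**Step 2. The second-retest row.** If the subject leaves the study, the Week 16 ACR50 is missing and counts as nonresponse. If IMP stops and the subject attends Week 16, the value follows an intercurrent event and also counts as nonresponse. Under the hypothetical estimand for continuous endpoints, the value is imputed in both cases. What changes is the treatment-policy analysis: an observed Week 16 value in one case, multiple imputation in the other.

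**Step 3. Size of the baseline-multiple gap.** The Table 12-3 entry point is the larger of 5xULN and 2 x Baseline. It exceeds 5xULN only when Baseline is above 5/2 = 2.5xULN. Exclusion 21a admits screening values below 3xULN. Assuming Baseline is similar to Screening, the upper limit is 2 x 3 = 6xULN. At Baseline 2.6 the entry point is 5.2; at 2.8 it is 5.6. The gap is therefore about 5 to <6xULN, for subjects with Baseline above 2.5xULN.

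**Step 4. TB timing.** The only scheduled on-study IGRA is at Week 12, which is also the last dosing visit (Day 1, Weeks 4, 8 and 12: four doses). Four weeks of prophylaxis from then reaches 12 + 4 = Week 16 at the earliest, when no dose is left. For such a subject, status depends on whether the stop is labelled a discontinuation, not on a missed dose.

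**Step 5. Effect on the primary comparison (illustration).** Inputs from Section 14.9.1: 26% vs 10%, 260 vs 130 subjects, two-sided 0.05, continuity-corrected chi-square. With p1 = 0.10, p2 = 0.26, k = 2 and d = 0.16:

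- Continuity correction: 130 = (n'/4)[1 + sqrt(1 + 2(1 + 1/k)/(n'd))]^2, which gives n' of about 120.8.
- Pooled rate: (0.10 + 2 x 0.26)/3 = 0.2067.
- z for power: [0.16 x sqrt(120.8) - 1.96 x sqrt(0.2067 x 0.7933 x 1.5)] / sqrt(0.10 x 0.90 + 0.26 x 0.74/2) = (1.758 - 0.972)/0.4315, about 1.82.
- Power: 96.6%. The stated 96% is reproduced.

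The Protocol gives no expected counts, so assume s bimekizumab responders become nonresponders (p2 = 0.26 - s/260) and placebo stays at 10%:

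| s | p2 | Power |
|---|---|---|
| 1 | 0.2562 | 95.9% |
| 2 | 0.2523 | 95.0% |
| 3 | 0.2485 | 94.1% |
| 5 | 0.2408 | 91.7% |
| 10 | 0.2215 | 82.7% |

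**The case against.** Three stronger readings are tempting, and the documents do not support them.

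- **That the passage followed always decides intercurrent-event status.** It does not at the second liver retest or for active TB, because IMP ends under either text.
- **That the repeat-test timing contradicts itself**, since 6.3.1 speaks of evaluation "with repeat tests performed in 2 weeks" and Table 12-3 says "Every attempt must be made to have repeat liver chemistry values and additional testing completed within 48 hours". Section 6.3.1 refers to Section 12.2.1 for the evaluation, and Table 12-3 has the same 2-week decision point with the same outcomes. A site can do both tests.
- **That 6.3.1 forbids the study withdrawal it orders.** The bar on withdrawal during work-up can be read as timing only. The conflict with Table 12-3 and the 6.3 lead-in remains.

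The best defence of the rest has four parts.

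- The rising-values rule can be seen as an addition, because a site that stops IMP breaches nothing in 6.3.1. That is fair, but a site working from 6.3.1 alone would not find the rule there.
- Item 10 could mean stopping first and judging later. However, it speaks of continuing, whereas item 13 speaks expressly of restarting.
- Item 9 requires permanent withdrawal only for active TB, or for latent infection with prophylaxis absent, stopped early or not followed, which fits later resumption. Section 5.4 also gives the ET Visit to subjects off IMP who stop attending. Both points hold, yet the ET Visit still marks the end of scheduled visits, which the lead-in says continue.
- An ET Visit held in place of Week 16 would still collect every ACR component (Section 8.3), and the SAP, not reviewed here, may settle classification. This limits the analytic harm but does not remove the conflicting site instructions.

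**Conclusion.** The conflicts are real and need correction, chiefly because sites cannot tell which action a mandatory safety rule requires. For the quoted liver sentence the statistical cost is confined to Week 16 data for the treatment-policy analysis; primary nonresponder status is the same either way, provided the IMP stop is recorded as a discontinuation before Week 16. Intercurrent-event status can differ in four situations only: rising liver values, the 5 to <6xULN baseline-multiple gap, IBD flares and latent TB. The effect on the primary result is likely small: one to three reclassified bimekizumab responders leave power at 94% or above. That range rests on assumed counts, since the Protocol gives no event frequencies, and on the planning rates of 26% and 10%. A reader might infer that the primary analysis is undermined; nothing in the documents supports that. No view is taken on which clinical rule is right.

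**What to change.** Reconcile the passages so that each condition has one threshold and one action, stated once and cross-referenced:

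- Section 6.3.1 with Table 12-3 and the Section 6.3 lead-in, including the twice-baseline qualifier and the rising-values rule;
- the two parts of item 10;
- item 9 with Sections 12.3.6.1 and 12.3.6.4, Figure 12-2 and the lead-in.

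For each, state whether the action is a temporary IMP interruption, IMP discontinuation or study withdrawal, and whether the Week 16 efficacy visit still takes place. In Section 14.3.1.1, state whether a temporary interruption counts as the intercurrent event. The clinical content is for the sponsor's medical team.

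The cost is amendment wording and a clarification letter to sites. No procedure or sample size changes.

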7 STUDY TREATMENTS

7.1 Description of investigational medicinal products

The IMPs used in this study are bimekizumab and placebo.

Placebo will be supplied as 0.9% sodium chloride aqueous solution (physiological saline, preservative-free) of pharmacopoeia (U.S. Pharmacopoeia/European Pharmacopoeia) quality in a 1mL PFS for sc injection.

Further details of the IMPs and their specification will be provided in the IMP Handling Manual.

7.2 Treatments to be administered

Unblinded study staff will be responsible for preparation of the clinical study material, including recording the administration information on source documents, and administration of the IMP as sc injections. The unblinded personnel will not be involved in the study in any way other than assuring the medication is taken from the correct kit and administering the IMP to the subjects. Suitable areas for sc injections are the abdominal wall, thigh, or upper outer arm without massage. On Day 1 (Baseline) one 160mg injection or one injection of placebo will be administered. Injection sites should be rotated between visits and injections should not be given in areas where the skin is tender, bruised, red, or hard.

An IMP Handling Manual will be provided to each site containing instructions regarding drug preparation and dosing.

Double-Blind Treatment Period dosing

During the Double-Blind Treatment Period, subjects will be randomized 2:1 to receive the following blinded IMP regimens: bimekizumab 160mg sc Q4W or placebo.

All subjects will receive 1 injection sc on Day 1 (Baseline) and 1 injection sc Q4W based on the following dosing scheme:

- Subjects randomized to receive bimekizumab will receive bimekizumab 160mg sc Q4W starting on Day 1 (Baseline).
- Subjects randomized to receive placebo will receive placebo injections sc Q4W starting on Day 1 (Baseline).

7.3 Packaging

The IMPs are manufactured, packaged, and labeled according to Good Manufacturing Practice (GMP) guidelines and applicable laws or regulations. Investigational medicinal products will be suitably packaged in such a way as to protect the IMPs from deterioration during transport and storage.

7.4 Labeling

Clinical drug supplies will be labeled in accordance with the current International Council for Harmonisation (ICH) guidelines on Good Clinical Practice (GCP) and GMP and will include any locally required statements. If necessary, labels will be translated into the local language.

7.5 Handling and storage requirements

Investigational Medicinal Products must be stored under refrigerated conditions (2°C to 8°C) protected from light. The IMPs must not be frozen.

The Investigator (or designee) is responsible for the safe and proper storage of IMP at the site. Investigational medicinal product stored by the Investigator is to be kept in a secured area with limited access according to the storage conditions mentioned on the label.

Appropriate storage conditions must be ensured either by controlling the temperature (eg, room, refrigeration unit) or by completion of a temperature log in accordance with local requirements on a regular basis, showing actual and minimum/maximum temperatures reached over the time interval.

In case an out-of-range temperature is noted, it must be immediately reported as per instructions contained in the IMP Handling Manual.

7.6 Drug accountability

A Drug Accountability form will be used to record IMP dispensing and return information on a by-subject basis and will serve as source documentation during the course of the study. Details of any IMP lost, damaged (due to breakage or wastage), not used, partially used, disposed of at the study site, or returned to the Sponsor or designee must also be recorded on the appropriate forms. All supplies and pharmacy documentation must be made available throughout the study for UCB (or designee) to review.

The packaging identifies each kit by a unique number that does not correlate to the contents and, therefore, does not unblind study site staff. Unblinded study staff will be responsible for preparation (eg, breaking tamper proof sticker on kit) of the clinical study material, including recording the administration information in the source document.

The Investigator (or designee) is responsible for retaining all used, unused, and partially used containers of IMP until returned or destroyed.

The Investigator must assign some of the Investigator's duties for drug accountability at the study site to an appropriate pharmacist/designee.

The Investigator must ensure that the IMP is used only in accordance with the protocol.

Periodically, and/or after completion of the clinical phase of the study, all used (including empty containers)/partially used, unused, damaged, and/or expired IMP must be reconciled and either destroyed at the site according to local laws, regulations, and UCB standard operating procedures (SOPs), or returned to UCB (or designee). Investigational medicinal product intended for the study cannot be used for any other purpose than that described in this protocol.

